2.1 Primary Objective

- To evaluate the safety and tolerability of subcutaneous (SC) blinatumomab dose administrations.

2.2 Secondary Objectives

- To determine pharmacokinetics (PK) with continuous intravenous (cIV) and SC administrations
- To estimate the maximum tolerated dose (MTD) tested for blinatumomab administered subcutaneously
- To determine the incidence of anti-blinatumomab antibody formation following SC administration
- To evaluate efficacy response following treatment with SC blinatumomab administration

2.3 Exploratory Objective

- To determine the pharmacodynamics (PD) time profiles for B- and T-lymphocytes as well as cytokine profiles during SC administration.
- To evaluate efficacy response following treatment with SC blinatumomab administration using Lugano criteria if positron emission tomography-computed tomography (PET/CT) is used for evaluation ([Appendix B](#))

3. Study Overview

3.1 Study Design

This is a global multi-center, Phase 1b open-label study investigating the safety and PK of blinatumomab administered subcutaneously for the treatment of relapsed/refractory indolent NHL. The SC administration of blinatumomab will be tested for the first time in humans.

Period 1 of the study will focus on the determination of PK, bioavailability, and safety profile of blinatumomab SC administration. The PK and bioavailability data from Period 1 of the study will be used in conjunction with safety data (DLT) to determine the SC

MTD. The MTD or the maximum tested dose, if MTD is not reached, will be further tested in Period 2 in an expanded cohort. Efficacy of blinatumomab administered subcutaneously will also be investigated in each period of the study.

3.1.1 Cycle 1/Period 1

In Period 1, 3 or more separate dose cohorts of up to 6 DLT evaluable subjects each will be enrolled and undergo treatment as follows:

- Subjects will undergo an initial cIV blinatumomab run-in period (weeks 1 to 3) followed by a 12-hour treatment free period.
- Subjects will then receive SC administration (week 4) followed by a treatment free period of 2 to not more than 3 days.
- After the SC administration period, subjects should return to receive cIV treatment to complete 6 weeks of therapy (weeks 5 to 6).

For all cohorts, the initial cIV dose of blinatumomab will be 9 µg/day for the first 7 days (to mitigate for potential cytokine release syndrome [CRS] and neurologic events associated with introduction to blinatumomab) which then will be escalated (dose-step) to 28 µg/day starting on day 8 through day 14 (week 2), and to 112 µg/day starting on day 15 until day 21 (week 3).

After stopping cIV blinatumomab, there is a 12-hour treatment free period before starting SC blinatumomab. SC blinatumomab starts after the 12-hour treatment free period and will be administered (week 4) as the following dose-cohort levels:

- Dose Cohort 1: 112 µg q12h × 5 days for a total of 9 doses (n= 6)
- Dose Cohort 2: 225 µg q12h × 5 days for a total of 9 doses (n = 6)

(Note: A total of 9 SC doses will be given for the q12h dosing, so intensive PK samples can be obtained on day shift to reduce errors).

- Dose Cohort 3: 450 µg q24h × 5 days for a total of 5 doses (n = 6)
- Additional Dose Cohorts: Dose level and dosing frequency to be determined as described below

One or more dosing regimens (refer to Dosing Schema Figure 1 in protocol) may be selected based on clinical findings including safety, tolerability, and PK results from previous cohorts; and after Dose Level Review Team (DLRT) review and make recommendations for the next SC cohort dose and frequency. The dose may be increased (by 1 dose level or between the dose of the previous cohort and the next higher dosing level in Figure 1 schema in protocol), kept at the same dose level or decreased by 1 or more dose levels. The dose frequency chosen (q12h, q24h, q48h,

q72h, q96h, or q7days) will be decided by the DLRT and will be based on the previous cohort PK data.

Once the SC dosing is complete, a treatment free period of 2 to not more than 3 days between stopping SC and restarting cIV will be observed. Then the cIV blinatumomab dosing will resume at 112 µg/day (weeks 5 to 6) to complete 6 weeks of treatment.

For each SC dose cohort, if ≤ 1 of the 6 DLT evaluable subjects experience a DLT during the SC administration DLT evaluation period then the dose will be determined to be tolerable and the DLRT will decide the next dose level to be initiated and the frequency of administration for the next cohort; see Section 6.2.1.2.2 in protocol for definition of the DLT evaluation period.

For each SC dose cohort, if ≥ 2 of the 6 DLT evaluable subjects experience a DLT during the SC administration then dosing will stop for individual subjects who experience a DLT, a DLRT meeting will be conducted, and further steps will be determined, such as dose de-escalation or increasing dosing interval (Figure 1 in protocol). In addition, if subjects on this cohort have not reached the SC dosing, they will be allowed to stay on study but will finish cycle 1/period 1 as cIV.

MTD will be defined as the highest dose level at which ≤ 1 of 6 subjects experience a DLT. If no subject experiences a DLT, the MTD will be defined as the maximal dose tested.

For further details, see Section 6.2.1.2.1 and Section 6.2.1.2.3 of protocol.

3.1.2 Cycle 1/Period 2

The aim of Period 2 will be to assess the MTD as derived from Period 1, or the maximum tested dose, if MTD has not been reached, for additional safety and preliminary efficacy data in an expanded cohort of up to 15 evaluable subjects receiving SC treatment only (no cIV run-in).

Doses for Cycle 1/Period 2 will be derived based on PK, bioavailability, and safety data collected in Cycle 1/Period 1 and DLRT review and recommendations. Subjects will receive sequentially the estimated SC doses equivalent to the 9 µg/day cIV in week 1, SC doses equivalent to the 28 µg/day cIV starting in week 1 and continuing into week 2, and then the SC doses of the selected maximal dose and dosing interval from Cycle 1/Period 1 starting in week 2 (day 12) and continuing to complete a total of 6 weeks of blinatumomab (see Section 6.2.1.2.2 in protocol for definition of the DLT evaluation period for Period 2).

3.1.3 Safety Monitoring

Safety monitoring will be implemented using continuous toxicity monitoring for early termination of the trial in Cycle 1/Period 2. Termination of study Cycle 1/Period 2 will occur if the posterior probability that the DLT rate is greater than 25%, given the cumulative data thus far, is at least 80%. Starting with the fifth subject treated in Cycle 1/Period 2, stopping may occur at any time.

The stopping boundaries assume a prior beta distribution of (0.50, 1.50) and a batch size of 1 (starting with the fifth subject treated) are presented in [Table 1](#) and the operating characteristics are given in [Table 2](#). The operating characteristics in [Table 2](#) provide the probability of stopping the trial early for given hypothetical true DLT (please see [section 6](#) for more details) rates whereas the stopping criteria in [Table 1](#) are based on situations where the empirical evidence would result in a posterior probability $\geq 80\%$ that the true DLT rate is $\geq 25\%$ ([Thall et al, 1995](#)).

Table 1. Cycle 1/Period 2 Stopping Boundaries

Cumulative Number of Subjects	Stop Study if This Many Subjects Have a Dose-limiting Toxicity
5 - 6	≥ 3
7 - 10	≥ 4
11 - 13	≥ 5
14	≥ 6
15	Study Period 2 is complete at 15

[figure not shown]
Note: Study may stop with fewer than 5 subjects if 3 or more subjects with DLTs have been observed

Table 2. Operating Characteristics

True Rate of Dose-Limiting Toxicities	Probability of Stopping Early	Average Sample Size
20%	17%	13.7
25%	30%	12.7
30%	45%	11.6
40%	72%	9.3
50%	90%	7.3
60%	98%	6.1

3.1.4 Study Schema

Figure 1. Study Schema for Cycle 1/Period 1: cIV Run-in and SC Dose

[figure not shown]

Abbreviations: cIV = continuous intravenous; DLRT = Dose Level Review Team; DLT = dose limiting toxicities; IP = investigational product; PK = pharmacokinetic; SC = subcutaneous; q12h = every 12 hours; q24h = every 24 hours, q48h = every 48 hours, q72h = every 72 hours, q96h = every 96 hours, q7d = every 7 days

**SC dose may be increased (by 1 dose level or between the dose of previous cohort and next higher dosing level), kept at the same dose level or decreased by 1 or more dose levels, and the dose frequency chosen (q12h, q24h, q48h, q72h, q96h, or q7days) will be decided by the DLRT and will be based on the previous cohort PK data.

- ❖ If $\geq 2/6$ DLT, then an immediate DLRT review will be conducted to determine next steps
- ❖ If $\leq 1/6$ DLT, then DLRT will be convened and next dose will be tested in a new cohort of subjects as outlined in the protocol

Figure 2. Study Schema for Cycle 1/Period 2

Abbreviations: MTD =maximum tolerated dose; PK = pharmacokinetic; SC = subcutaneous

3.2 Sample Size

Approximately 54 subjects will be enrolled in this study in order to ensure approximately 30 evaluable subjects in Period 1 and up to 15 evaluable subjects in Period 2 are treated with blinatumomab. Subjects may be replaced (replacement rules outlined in protocol Section 3.4). This sample size is based on practical considerations and is consistent with conventional phase 1 oncology studies. If the true DLT rate is 10%, there is a 89% probability of observing ≤ 1 DLT and 11% probability of observing 2 or more DLT in 6 subjects. If the true DLT rate is 30%, the probability of observing ≤ 1 DLT decreases to 42% and probability of observing 2 or more DLT increases to 58%.

Up to 15 evaluable subjects will be enrolled into Cycle1/Period 2 with the planned target treatment dose being the highest tolerable dose regimen or highest tested dose regimen based on the DLRT's recommendations. There will be interim look at the cumulative data in this period and based on the toxicity observed, early termination of the trial in Cycle 1/Period 2 will occur. For example, with 14 subjects receiving AMG 103 SC doses in Cycle 1/Period 1, there is a 17% chance of early termination if the true DLT rate is

20% and with a true DLT rate of 30% increases the chance of early termination to 45% when the sample size is 12. Early termination rules are detailed in section [Table 2](#).

4. Study Endpoints and Covariates

4.1 Study Endpoints

4.1.1 Primary Endpoint

- Subject grade, incidence, and severity of dose limiting toxicities (DLTs) and adverse events

4.1.2 Secondary Endpoints

- Blinatumomab PK parameters under cIV and SC administrations
- MTD
- Incidence of anti-blinatumomab antibodies
- Overall response rate (ORR) (complete response [CR] + partial response [PR]) as determined by best overall response ORR using Cheson criteria (see [Appendix B](#))

4.1.3 Exploratory Endpoint

- PD parameters of B- and T-lymphocytes and cytokines following administration of SC blinatumomab
- ORR (CR + PR) as determined by best overall response using Lugano criteria (see [Appendix C](#))

4.2 Planned Covariates

The relationship of the certain baseline covariates to endpoints will be explored if appropriate. Biomarker data may be incorporated in additional exploratory subgroup or multivariate analyses. The analyses of biomarkers may be performed after collection of all samples during the conduct of the study and therefore may be reported after the final analysis.

5. Hypotheses and/or Estimations

No formal statistical hypothesis will be tested.

The clinical hypothesis is that blinatumomab administered through the SC route will demonstrate a tolerable safety-profile with serum concentrations comparable to those for which efficacy was shown with cIV administration in subjects with indolent relapsed/refractory Non-Hodgkin's Lymphoma (NHL).

6. Definitions

Age at Enrollment

Subject age at enrollment will be collected in years in the clinical database.

Baseline

For the analysis of all endpoints, baseline will be defined as the value measured on day 1 of the first cycle of blinatumomab. If a day 1 value is not available, the most recent value before the day of the start of any protocol-specified therapy may be used.

Best Overall Response

Best overall response for a subject is determined as ORR (CR+PR) using Cheson ([Appendix B](#)) and Lugano criteria ([Appendix C](#)) during the Safety Follow-up visit (2 to 4 weeks after the end of therapy for cycle 1). In the case where a second cycle is administered, the assessment has to be done prior to the start of the next cycle to assess the evolution of disease (as close to 2 weeks after the last dose of IP cycle 1, but before starting cycle 2).

Change From Baseline

Change from Baseline is the arithmetic difference between post-Baseline and Baseline values.

Disease Related Events

Disease Related Events are events (serious or non-serious) anticipated to occur in the study population due to the underlying disease eg, disease progression ([Table 3](#)). Such events do not meet the definition of an adverse event unless assessed to be more severe than expected for the subject's condition.

Disease Related Events that do not qualify as Adverse Events or Serious Adverse Events:

- An event which is part of the normal course of disease under study (eg, disease progression in oncology or hospitalization due to disease progression) is to be reported as a Disease Related Event.
- Death due to the disease under study is to be recorded on the event CRF.

If the outcome of the underlying disease is worse than that which would normally be expected for the subject, or if the investigator believes there is a causal relationship between the IP(s)/study treatment protocol required therapies and disease worsening, this must be reported as an adverse event or a serious adverse event. [Table 3](#) outlines the expected Disease-Related Events by System Organ Class (SOC).

Table 3. Disease-related Adverse Events by System Organ Class

System Organ Class (SOC)	Preferred Terms
Blood and lymphatic system disorders	Lymphadenopathy
General disorders and administration site conditions	Disease progression Fatigue
Investigations	Weight decreased
Skin and subcutaneous tissue disorder	Night sweats

Disease Related Events that would qualify as an Adverse Event or Serious Adverse Event:

- An event based on the underlying disease that is worse than expected as assessed by the investigator for the subject's condition or if the investigator believes there is a causal relationship between the investigational product(s)/study treatment/protocol-required therapies and disease worsening, this must be reported as an Adverse Event or Serious Adverse Event.

DLT Evaluable

Period 1:

To be evaluable for DLT, subjects must meet one of the following criteria:

- Cohort I and II: received treatment for or at least 8 of the 9 doses or experienced a DLT at any time while receiving blinatumomab.
- Cohort III: treated at least 4 of the 5 doses or experienced a DLT at any time while receiving the target dose of blinatumomab.

If a subject does not experience a DLT during the DLT evaluation period and does not receive all doses (q48h, q72h, q96h, or q7d dosing), at least 4 of the 5 doses (q24h dosing) or at least 8 of the 9 doses (q12h dosing) of subcutaneous Blinatumomab and taken off study for reasons other than toxicity the subject will not be considered DLT-evaluable and will be replaced as described in Protocol Section 3.4.1.

Period 2:

To be evaluable for DLT, subjects must meet one of the following criteria:

- If only cycle 1 is given : experienced a DLT during the entire duration of the SC administrations and 30 days after the last SC dose or treated with blinatumomab targeted dose for 5 days.
- If cycle 2 is given: experienced a DLT during the entire duration of the SC administrations and 16 days following the last SC dose or until the start of cycle 2 (whichever is longer), up to 30 days after the last SC dose or treated with blinatumomab at 112 µg/day cIV for 42 days.

Dose Limiting Toxicity (DLT)

The occurrence of any of the toxicities mentioned in the section 6.2.1.2.3 of the protocol will be considered a DLT, if judged by the investigator to be related to administration of blinatumomab.

ECOG Performance Status Assessment

ECOG performance status assessment will be performed using the ECOG score. For more details please refer appendix C in Protocol.

End of Study for Individual Subject

End of IP Administration for subjects who had blinatumomab is defined as the date the decision was made to end IP as recorded on the End of IP CRF page.

End of Treatment

Defined as the last assessment for the protocol-specified treatment phase of the study for an individual subject.

End of Follow-up

Defined as the date that the last subject completes the last protocol-specified assessment in the study.

Enrollment Date

Enrollment Date is defined as the date of enrollment collected on the CRF.

Subject Level End of Study (EOS) Date

End of study for each subject is defined as the date the subject last completed a protocol-specified procedure. The date will be recorded on the End of Study CRF page.

Investigational Product

The term 'investigational product' is used in reference to blinatumomab.

Last Dose Date of Investigational Product

This is the stop date of the last dose of blinatumomab administration reported on the Investigational Product Administration CRF.

Maximum Tolerated Dose (MTD)

MTD will be defined as the highest dose level at which ≤ 1 of 6 subjects experience a DLT. If no subject experiences a DLT, the MTD will be defined as the maximal dose tested.

Optional Cycle 2

A subject may receive a second cycle of blinatumomab administered SC if the subject derived clinical benefit (demonstrated on staging scans) from Cycle 1/Period 2 treatment. If no clinical benefit occurred with SC in Cycle 1/Period 2 then an optional Cycle 2/Period 2 may still be given but will administered as a cIV infusion instead of SC. If blinatumomab is administered as a cIV infusion it will be dosed at 9 $\mu\text{g/day}$ cIV for 7 days for days 1 through day 7, next the dose will be escalated (dose step) to 28 $\mu\text{g/day}$ cIV for 7 days starting on day 8 through day 14, and then advanced to 112 $\mu\text{g/day}$ cIV for 28 days starting on day 15 through day 42.

Percent Change From Baseline

Percent change from Baseline is the arithmetic difference between post-Baseline and Baseline divided by Baseline values times 100.

Screened

A subject is considered in screening once a consent form has been signed.

Study Day 1

Study day 1 is defined as the first day of administration of the investigational product after enrollment. The day prior to Study Day 1 is considered Day -1.

Study Day

Post study day 1: study day= (date - date of Study Day 1) + 1

Pre study day 1: study day= (date – date of Study Day 1)

Study Duration

For an individual subject, the length of participation includes a 14 day screening period, up to a 14 week treatment period (6 weeks for cycle 1 in Period 1 and Period 2 and 6 weeks for the optional Cycle 2, separated by a 14 day treatment free interval), and a safety follow-up visit (30 days [+ 7 days] after the last dose of study treatment).

For subjects who complete the protocol from the date of first dose through optional Cycle 2, the entire duration of the study will take approximately 20 weeks to complete. However, individual study duration will vary depending on administration of a second cycle and tolerability of blinatumomab by an individual subject.

Treatment emergent adverse events (TEAEs)

A treatment emergent adverse event refers to the adverse event that starts on or after first dose of blinatumomab through 30 days after the last dose of blinatumomab. It is indicated by the flag whether an event start before first dose of blinatumomab on the Event CRF page. This reporting window also applies to treatment-emergent serious adverse events (SAEs).

7. Analysis Subsets

The analysis of all endpoints, unless noted otherwise, will be conducted on the Full Analysis Set defined in [Section 7.1](#).

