### 3.4 Replacement of Subjects

Subjects enrolled may be replaced if they are not evaluable for DLT during the DLT observation period as described in [Section 6.2.1.2.2](#).

#### 3.4.1 Replacement Rules in Cycle 1/Period 1

Subjects may be replaced for any of the following reasons:

- failing to complete all 3 cIV dosing levels during cIV run-in (weeks 1 to 3)
- failure to receive **all doses (q48h, q72h, q96h, or q7d dosing)**, at least 4 of the 5 doses (q24h dosing), or at least 8 of 9 doses (q12h dosing) during the SC treatment period (week 4)
- withdrawal from study for DLT without having had PK assessments (subjects who withdraw due to DLT are evaluable from a safety standpoint, but may not be evaluable from a PK standpoint if they have not completed their PK blood draws)
- subjects may be replaced if they miss the PK assessment time point and are unable to resume dosing and PK assessments
  - Note: Subjects who miss a dose before any PK assessments will default to the day of the missed dose. PK assessments will be performed per [Table 4](#) following the subject's resumed dose of investigational product (IP). For example, if a subject misses the dose on study day 2, the restart treatment day will be considered as study day 2 and all applicable assessments will be done per Schedule of Assessments (refer to [Table 3](#) and [Table 4](#) for further details)
- for all subjects who miss PK samples, the PK scientist will evaluate the PK results for this subject, and determine if the subject needs to be replaced, or if the PK results are sufficient for analysis. The DLRT will be informed of this decision to replace or not replace individual subjects at the time of the DLRT meeting.
  - subjects who do not complete PK assessments may continue on study, even if replaced

#### 3.4.2 Replacement Rules in Cycle 1/Period 2

Subjects may be replaced for any of the following reasons (except subjects removed for DLT that will never be replaced):

- failure to receive **at least 85% of the first 8 planned doses during the SC treatment period as outlined in [Table 6](#) (this would include 5 doses of step dose run-in and 3 doses at MTD)**

Approved

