#### 6.2.1.2.2 Dose Limiting Toxicity Rules

##### Cycle 1/Period 1

The DLT evaluation period includes the entire **week 4 (7 days) which is the week that blinatumomab is administered** SC during Cycle 1/Period 1 of the study. To be evaluable for a DLT, subjects must have experienced a DLT within the DLT evaluation period. In addition, if the investigator and/or sponsor removes the subject from the study due to a treatment-related toxicity during the DLT evaluation period, regardless of the grade of toxicity, this will be considered a DLT. If a subject does not experience a DLT during the DLT evaluation period and does not receive **all doses (q48h, q72h, q96h, or q7d dosing)**, at least 4 of the 5 doses (q24h dosing), or at least 8 of 9 doses (q12h dosing) of **SC** blinatumomab during Cycle 1/Period 1 of the study, the subject will not be considered DLT-evaluable and will be replaced as described in [Section 3.4.1](#).

If  $\leq 1$  of the 6 evaluable subjects in a dose SC cohort experience a DLT during the SC administration, then the dose will be determined to be tolerable and the next dose-cohort level will be initiated in a new dose-cohort of subjects after review by the DLRT.

If  $\geq 2$  subjects of the 6 evaluable subjects in a SC dose cohort experience a DLT during SC administration then dosing will stop for individual subjects who experience a DLT, a DLRT meeting will be conducted, and further steps will be determined.

Additionally, the DLRT will meet:

- once dose-cohort 1 has completed subcutaneous dosing
- once dose-cohorts 2 and 3 have completed subcutaneous dosing
- once any additional cohorts complete dosing if additional dose-cohorts are tested to determine the MTD in Cycle 1/Period 1

## Cycle 1/Period 2

For subjects who receive optional Cycle 2 after Cycle 1/Period 2 (SC dosing period), the DLT evaluation period includes the entire duration of SC administration **in Cycle 1** and 16 days following the last SC dose (56 days in total) or until the start of optional Cycle 2, whichever is longer, up to 30 days after the last SC dose **of Cycle 1**.

For subjects who do not receive optional Cycle 2, the DLT evaluation period includes the entire duration of SC administration and 30 days following the last SC dose (70 days in total).

Continuous monitoring for early termination of the trial will be performed (refer to [Section 10.2](#)).

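### The SAP excludes an under-dosed Period 1 subject without a DLT only if the subject also left the study; the protocol has no such condition, and for the longer-interval cohorts the SAP gives no other rule

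*SAP*

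**What the plan says.** **Protocol section 6.2.1.2.2, Period 1.** Exclusion has two conditions, no DLT and too little SC dosing: "If a subject does not experience a DLT during the DLT evaluation period and does not receive" the minimum number of SC doses, "the subject will not be considered DLT-evaluable and will be replaced as described in" section 3.4.1. The minimums are 8 of 9 doses (q12h), 4 of 5 (q24h) and all doses (q48h, q72h, q96h, q7d). Leaving the study plays no part. A DLT makes a subject evaluable if it falls in the evaluation period, which is week 4: "To be evaluable for a DLT, subjects must have experienced a DLT within the DLT evaluation period".

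**SAP section 6, DLT Evaluable, Period 1.** This has two layers.

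- Inclusion bullets, of which a subject must meet one. For Cohorts I and II (q12h) the bullet reads "received treatment for or at least 8 of the 9 doses or experienced a DLT at any time while receiving blinatumomab". The bullet for Cohort III (q24h) has the same form, with a minimum of 4 doses out of 5 and a DLT accepted whenever the subject is on the target dose. There is no bullet for any additional cohort.
- An exclusion sentence that covers all dosing frequencies with the protocol's minimums, but requires in addition that the subject be "taken off study for reasons other than toxicity the subject will not be considered DLT-evaluable".

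**Which text governs.** SAP section 7.3 defines the DLT analysis set by pointing to section 8.1.1.2, which points back to section 6. Section 10.5.1.1 uses that set. SAP section 11 reports no change from the protocol's analyses.

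**The concern.** The DLT analysis set is the denominator for the DLT component of the primary endpoint, and DLT-evaluable subjects are the six to whom the at-most-1-of-6 rule applies. A subject who received too little SC drug and had no DLT says little about the tolerability of the regimen. Counting that subject as one of six non-events pulls the observed rate down and makes a regimen easier to declare tolerable. The protocol prevents this by replacing the subject. The SAP's exclusion sentence, taken alone, does not do so when the subject remains on study.

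The two documents also differ on timing. For Cohorts I and II the SAP accepts a DLT at any time on blinatumomab, which can be read to include the cIV weeks; the protocol accepts only week 4.

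**Working it through.** **1. The rules side by side: a subject with no DLT, too few SC doses, still on study**

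| Cohort | Protocol 6.2.1.2.2 | SAP inclusion bullets | SAP exclusion sentence |
|---|---|---|---|
| 1 and 2 (q12h), 3 (q24h) | Not evaluable | Fails the bullet: not evaluable | Does not exclude |
| Additional q48h, q72h, q96h, q7d | Not evaluable | No bullet | Does not exclude |

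The first row is an internal contradiction in the SAP. The second is a gap.

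**2. Can such a subject exist?** Yes. Protocol section 8.1 lets a subject decline investigational product and remain in the study. Section 8.3.1 lists adverse events among the reasons for removal from treatment. Section 8.3.2 confines removal from the study to sponsor decision, withdrawn consent, death and loss to follow-up. Under section 6.2.1.2.3 a grade 3 neurologic event that resolves to grade 1 or less within 7 days is not a DLT, yet Table 2 interrupts SC dosing for it. Removal from the study for related toxicity does not create the problem, because the protocol counts it as a DLT ("if the investigator and/or sponsor removes the subject from the study due to a treatment-related toxicity during the DLT evaluation period").

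**3. The plan's own figures.** Protocol section 10.2 and SAP section 3.2 give the chance of at most 1 DLT in 6 subjects as 89% at a true rate of 10% and 42% at 30%. With P(pass) = (1−p)^6 + 6p(1−p)^5:

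- p = 0.10: 0.5314 + 0.3543 = 0.886
- p = 0.30: 0.1176 + 0.3025 = 0.420

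Both reproduce.

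**4. Effect of under-dosed subjects among the six.** Let one subject have DLT risk q and the other five risk p:

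P(pass) = (1−p)^5 + 5p(1−p)^4 × (1−q)

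At p = 0.30 the two terms are 0.1681 and 0.3602 × (1−q).

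- Half risk, q = 0.15: 0.1681 + 0.3602 × 0.85 = 0.474
- No risk, q = 0: 0.1681 + 0.3602 = 0.528
- Two subjects at no risk: (1−p)^4 + 4p(1−p)^3 = 0.2401 + 0.4116 = 0.652

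| True DLT rate | Six fully exposed | One at half risk | One at no risk | Two at no risk |
|---|---|---|---|---|
| 10% | 88.6% | 90.2% | 91.9% | 94.8% |
| 30% | 42.0% | 47.4% | 52.8% | 65.2% |
| 40% | 23.3% | 28.5% | 33.7% | 47.5% |

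**5. Which column is plausible?** Protocol Table 4 schedules three SC doses for q48h, two for q72h and q96h, and one for q7d. Assume that risk accrues evenly per dose, so that q = 1 − 0.7^f, where f is the fraction of doses received.

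- q48h, 2 of 3 doses: q = 0.212, P(pass) = 0.1681 + 0.3602 × 0.788 = 0.452
- q72h or q96h, 1 of 2 doses: q = 0.163, P(pass) = 0.1681 + 0.3602 × 0.837 = 0.469

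For q7d the only under-dosed subject is one with no SC dose, which is the no-risk column. The documents give neither the number of such subjects nor their residual risk.

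**The case against.** Several stronger readings are tempting, and most of the case against them stands.

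- **That the SAP admits under-dosed subjects in every cohort.** It does not clearly do so in Cohorts 1 to 3. A sentence naming one non-evaluable group does not make everyone else evaluable, and the bullets that a subject must meet remove these subjects. What remains there is conflicting drafting.
- **That the protocol makes only DLT cases evaluable, so that every DLT rate would be 100%.** One sentence read alone says so. The same section then supplies the dose criterion and applies a rule of at most 1 DLT among 6 evaluable subjects, which would make no sense on that reading.
- **That the protocol expressly allows missed SC doses with continuation on cIV.** The statement in section 3.4.1, "subjects who do not complete PK assessments may continue on study, even if replaced", concerns PK sampling. Subjects moved to cIV after two DLTs (end of section 6.2.1.4.2) belong to a cohort that has already failed the rule, so they cannot help it pass. The support is the separation of treatment from study in section 8.
- **That a toxic regimen would in practice be passed.** The DLRT sees individual dosing and adverse-event listings (SAP Appendix F), and the protocol tells it to replace these subjects. Table 2 also has subjects resume SC after many interruptions, which makes the case less frequent. This limits the practical risk but does not repair the SAP definition, on which the reported DLT incidence will be based.
- **That 53% or 65% is the expected effect.** These are upper bounds. They assume no DLT risk in the under-dosed subjects.

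**Conclusion.** The two documents define the Period 1 DLT-evaluable set differently, and SAP section 11 does not disclose it. For additional q48h, q72h, q96h or q7d cohorts the SAP's only rule fails to exclude an under-dosed subject without a DLT who stays on study. For Cohorts 1 to 3 the SAP contradicts itself, with the bullets giving the protocol's answer. The window for a qualifying DLT in Cohorts I and II is also wider in the SAP than in the protocol.

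The discrepancy reaches only the DLT component of the primary endpoint and the at-most-1-of-6 rule; adverse events are analysed on the full analysis set. At a true rate of 30% a single retained subject moves the chance of passing by about 5 points at half risk and by at most 11 (42% to 53%). Two move it by at most 23 (42% to 65%). These sizes illustrate direction and order of magnitude under assumed counts and risks. The point should be corrected; it is not a flaw in the design.

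**What to change.** In SAP section 6, delete the condition about being taken off study for non-toxicity reasons, and replace the cohort-numbered bullets with one definition that covers every dosing frequency and matches the protocol. A Period 1 subject is DLT-evaluable if the subject either

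- had a DLT within the week 4 evaluation period, or
- received the protocol's existing minimum of SC doses: 8 of 9 for q12h, 4 of 5 for q24h, all for longer intervals.

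This also removes the difference in the DLT window. As tidying only, reword the protocol's sentence on having experienced a DLT so that it states the same two alternatives.

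The cost is wording in two places, plus an occasional replacement for which the protocol already provides.
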